A growing body of research shows that HRV biofeedback training not only increases HRV but also reduces symptoms of stress and anxiety with a large standardized effect size in a meta-analysis of 24 studies.[9] The intervention is believed to restore autonomic balance by increasing activity in the vagus nerve, which underlies activation of the parasympathetic branch of the autonomic nervous system. Pilot studies have revealed that HRV training specifically reduces PTSD symptoms in traumatized people[10] and reduces anxiety in cardiac patients.[11] These intervention findings are in line with the reliable correlational finding that higher HRV has been associated with lower negative affect, even after controlling for respiration rate, demographic characteristics, exercise, smoking, and medications that affect cardiac activity.[12] Critically, in a randomized controlled study, HRV biofeedback training using the same hardware and smartphone app as in the present study has been shown to lower resting heart rate by over 5 beats per minute and increase HRV by over 30%.[13]

Research is needed to determine whether HRV training has beneficial consequences for mental and cardiovascular health in patients who have experienced serious cardiac events. Cardiac arrest survivors, in particular, may benefit from such an intervention because many of them experience clinically significant psychological distress after their medical event.[14] An important research question for this population concerns the best ways to maximize the efficacy of HRV training on fear outcomes. The currently predominant version of HRV training was developed two decades years ago by Paul Lehrer and colleagues.[7] It involves identifying for each individual the respiratory rate at which their variability in beat-to-beat heart rate (HR) is maximized. For many people, this rate tends to be approximately 0.1 Hz (i.e., breaths per second), which amounts to 6 breaths/minute. Participants then practice breathing at this rate with the goal of improving their post-training resting state HRV. It has been proposed that the training achieves its dampening effects on fear, stress, and anxiety by enhancing the baroreflex and increasing vagal afferent traffic to frontal cortical brain regions associated with affective regulation.[15]

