We will recruit 10 participants who each recently survived a cardiac arrest and who are either 1) participating in a separate ongoing longitudinal study (Cardiac Arrest Neuropsychological Outcomes Evaluation [CANOE]; IRB Protocol #: AAAR8497) or 2) on a mailing list to receive information from the Sudden Cardiac Arrest Foundation (SCAF), a community of cardiac arrest survivors, their families, and other advocates. They will complete a brief set of screening questions to determine eligibility. They will complete three “Video Visits” that will be conducted by study staff who will meet with the participant via the Zoom application associated with Columbia University Irving Medical Center, 1) an enrollment video visit within 72 months since their cardiac arrest, 2) a baseline/pre-intervention video visit approximately a week after the enrollment video visit (once participant confirms receiving study materials), and 3) a post-intervention video visit 3 weeks after the pre-intervention video visit. The first video visit will last approximately 45 minutes, the second video visit will last approximately 60 minutes and the third video visit will last approximately 30 minutes.

Upon obtaining verbal consent, the first video visit includes demographic and partner/caregiver questionnaires, download of the smartphone app (Elite HRV), and selection of appropriate chest strap size for the heart rate monitor for the participant.

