Participants begin each session by applying water to the electrode strip on the Polar H10 heart rate monitor, clipping the transmitter portion of the device to its strap, and then attaching the strap around their torso over the lower portion of their ribcage. They sit in a comfortable, relaxed, and well supported position. They open the Elite HRV app on their smartphone (iPhone or Android) and verify that it has connected successfully to the heart rate monitor via Bluetooth. Participants select the “Open Reading” option in the app. After a brief stabilization period of several seconds, the training task begins. Participants see the following on the screen: 1) a breathing pacing stimulus: a circle that continually expands for 5 seconds and then contracts for 5 seconds, 2) a numerical readout of current heart rate, 3) a numerical readout of their current heart rate variability, 4) a visual representation of their increasing and decreasing heart rate over the last minute, 5) a running tally of the time elapsed in the training session. Participants are instructed to breathe in as the circle expands, and breathe out as the circle shrinks. They are told to watch as a line shows their heart rate going up and down. Participants are instructed that their goal is to try to make large, slow changes in heart rate that follow the pace of their slow breathing instead of the smaller, faster changes in heart rate that occur when they are not doing the training exercise. When the timer indicates that 10 minutes have passed (or at least 5 minutes), then participants end the training session. Detailed instructions are provided to participants with these instructions, and all the steps are also covered with the experimenters present during the second video visit.

Participants are asked to select the option to export their data using the Elite HRV app after each session. The transmitted data come to the specified email address (see above) as a zipped directory. The name of that zipped directory includes only the participant’s study ID and does not contain any identifiable information. The directory includes a separate text file for each recording session (i.e., each training session) with only the date and times of the recording in the file name. Each text file contains only a list of numeric values that represent the intervals elapsed in milliseconds between consecutive heartbeats during the recording.

3rd (Post-Intervention) Video Visit (30 minutes)

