- (7) Elevated post-traumatic stress disorder (PTSD) symptom total scores on the 17-item Post-Traumatic Stress Disorder Checklist (PCL) of 30 or higher (i.e., greater than the median in a prior sample of cardiac arrest survivors) or elevated PCL-5 scores of 30 or higher or Acute Stress Disorder Scale (ASDS) scores of 34 or higher
- (8) Owns either an iPhone or Android smartphone in order to run the app involved in the intervention

Exclusion criteria

- (1) Breathing difficulty that does not allow participant to complete the intervention
- (2) Inability to comply with the protocol (either self-selected or indicated during screening that s/he could not complete all requested tasks). This includes, but is not limited to, patients with a level of cognitive impairment indicative of dementia and patients with current alcohol or substance abuse, patients with severe visual impairment, patients with severe auditory impairment, and patients with severe mental illness (e.g., schizophrenia).

For non-CANOE cardiac arrest survivors who respond to our study flyer online:

Inclusion criteria

- (1) Age 18 years or older
- (2) Fluent in English
- (3) A self-reported diagnosis of cardiac arrest (CA)
- (4) Time elapsed since their CA is less than 72 months
- (5) Elevated PCL-5 scores of 30 or higher
- (6) Owns either an iPhone or Android smartphone in order to run the app involved in the intervention

Exclusion criteria

- (1) Breathing difficulty that does not allow participant to complete the intervention
- (2) Inability to comply with the protocol (either self-selected or indicated during screening that s/he could not complete all requested tasks). This includes, but is not limited to, patients with a level of cognitive impairment indicative of dementia, patients with current alcohol or substance problems, patients with severe visual impairment, patients with severe auditory impairment, and patients with severe mental illness (e.g., schizophrenia).

6. Risks

There are minimal risks involved with completing the HRV training and the questions about emotions and state anxiety. The questions asked and the thoughts evoked during the course of this research study pose minimal risk of psychological discomfort, and some participants may wish to skip any question or

questionnaire that they choose. Participants will be made aware of these risks, and will be assured they can terminate their participation in the study at any time without penalty.

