Exploratory Aims: *(1) To assess whether HRV increases over the course of the at-home training sessions across participants (measured as the natural log of the root mean square of the successive difference [lnRMSSD]). (2) To assess whether individual differences in the slope of change in HRV over the course of the study is positively associated with the magnitude of reduction in cardiac-related interoceptive fear, trait anxiety, or negative affect.*

Statistical approach for Exploratory Aims. (1) We will use participants' exported and deidentified HRV data to compute lnRMSSD, a standard measure of beat-to-beat HRV. For each participant, we will use a linear regression equation to find the line of best fit that represents the slope of HRV change over time for all available training sessions where time (day since baseline) is the predictor and HRV is the outcome. We will assess what proportion of participants show a positive slope (> 0). (2) We will correlate this slope with the Visit-2-to-3 change in cardiac-related interoceptive fear, the Visit-2-to-3 change in trait anxiety, and the Visit-2-to-3 change in negative affect.

Planned Interim Analyses. Given the relatively small sample size of this study ($N = 10$ participants) and the expected minimal risk of HRVB, interim analyses will not be planned. Nevertheless, if concerns arise related to adverse events, as outlined in the data safety monitoring plan, then an unblinded interim analysis may be conducted, and the trial may be stopped early.

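### Neither eligibility list asks about heart rhythm or pacing, so lnRMSSD slopes that do not measure vagal training could enter the exploratory HRV analyses

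*Protocol*

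**What the plan says.** **Eligibility (Protocol section 5).** Both routes, the parent cohort and the online flyer, carry the same two kinds of exclusion. The first is "Breathing difficulty that does not allow participant to complete the intervention". The second is inability to comply, either self-selected or brought out at screening. Its examples are dementia-level cognitive impairment, alcohol or substance problems, severe visual or auditory impairment, and severe mental illness. The list of examples is open-ended, but none is cardiac. On the online route the cardiac arrest itself is self-reported.

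**The task (Protocol section 3, HRV Biofeedback Training).** Participants breathe with a pacing circle while watching their heart rate, and are told that "their goal is to try to make large, slow changes in heart rate that follow the pace of their slow breathing". Protocol section 1 reports a proposal that "the training achieves its dampening effects on fear, stress, and anxiety by enhancing the baroreflex and increasing vagal afferent traffic" to frontal brain regions.

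**The data (same section).** Each exported file holds only the times between successive heartbeats. The Measures part of section 2 adds demographics and partner or caregiver status, but no cardiac history.

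**The analysis (SAP, Statistical approach for Exploratory Aims).** lnRMSSD is computed from the exports. A straight line against day since baseline is fitted for each participant, using whatever training sessions are available. Then: "We will assess what proportion of participants show a positive slope (> 0"). The slope is also correlated with the Visit 2 to Visit 3 change in interoceptive fear, trait anxiety and negative affect. No rule on rhythm is stated.

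**The concern.** The training response is a heart rate that rises and falls with slow breathing, and lnRMSSD is used as its measure. Both presuppose a rhythm that the vagus nerve can modulate. In persistent or permanent atrial fibrillation the beat intervals are irregular whatever the breathing. With continuous pacing they are largely set by the device. This is general physiology that the documents do not state, but it follows from what the measure is. A study that enrols only cardiac arrest survivors has reason to ask.

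The protocol already accepts that some people cannot carry out the intervention, and screens for breathing difficulty. It does not extend that thought to the heart rhythm on which the feedback depends. At stake is the meaning of the two exploratory HRV results. A slope that reflects rhythm or device behaviour would be counted as a rise or fall in trained HRV. It would also be one of at most 10 points in each correlation. The omission is hard to repair afterwards, because beat intervals without a tracing or device record do not reliably establish the rhythm.

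**Working it through.** **1. The plan's own recruitment figure.** The SAP gives the number to approach in order to enrol 10, at agreement rates of 40%, 50% and 60%. Number = 10 / rate, rounded up: 10/0.4 = 25; 10/0.5 = 20; 10/0.6 = 16.7, so 17. These match the SAP. They stay the same if rhythm is only recorded. If it became an exclusion applied after approach, with an assumed 10% affected, the number would be 10 / (rate × 0.90): 27.8, 22.2 and 18.5, so 28, 23 and 19.

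**2. Chance that the problem arises.** Inputs: n = 10 (Protocol section 2); q = share of eligible survivors in persistent or permanent atrial fibrillation or paced all or most of the time. The documents give no value for q, so a range is assumed, with participants treated as independent.

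P(at least 1) = 1 − (1 − q)^10; P(at least 2) = P(at least 1) − 10q(1 − q)^9; expected number = 10q.

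| Assumed q | Expected number of 10 | P(at least 1) | P(at least 2) |
|---|---|---|---|
| 2% | 0.2 | 1 − 0.98^10 = 18% | 2% |
| 5% | 0.5 | 1 − 0.95^10 = 40% | 9% |
| 10% | 1.0 | 1 − 0.90^10 = 65% | 26% |
| 20% | 2.0 | 1 − 0.80^10 = 89% | 62% |

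**3. Effect on the proportion with a positive slope.** Suppose one of 10 is affected and 6 of the other 9 have positive slopes (an illustration, not a forecast). The interpretable result is 6/9 = 67%. Under the SAP rule it is reported as 7/10 = 70% or 6/10 = 60%, depending on a slope that carries no information on training.

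**4. Effect on the correlations.** The SAP names no significance test for them. As a gauge of precision only, the |r| needed for two-sided p < 0.05 is t / √(n − 2 + t²), where t is the 97.5% point on n − 2 degrees of freedom.

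| Affected | Interpretable n | \|r\| needed |
|---|---|---|
| 0 | 10 | 0.63 |
| 1 | 9 | 0.67 |
| 2 | 8 | 0.71 |
| 3 | 7 | 0.75 |

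Leaving affected participants out therefore costs little precision in an analysis that has little to begin with. Keeping them in gives the appearance of n = 10 while some points do not measure the predictor.

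**The case against.** The case against going further is substantial, and most of it stands.

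- **No prevalence.** At q = 5% the likeliest outcome is that none of the 10 is affected (0.95^10 = 60%); at 2% that chance is 82%. A reader might infer that some of the 10 are bound to be affected. The documents do not support that.
- **The session can still be done.** An affected person can wear the strap, breathe with the circle, stop after 5 to 10 minutes and export. The compliance measure (at least 8 of 15 sessions) needs no HRV response. It would be wrong to say such a person cannot perform the task; what may be missing is the trained response.
- **Aim 1 is largely untouched.** A reader might infer that each affected person moves every Aim 1 proportion by 10 points. Measure 1 is taken over those approached, so one person is 1/25 to 1/17, or about 4 to 6 points. Measures 2 and 3 do not depend on rhythm. Measures 4 to 7 change only if rhythm pushes a rating across its threshold, which nothing in the documents shows.
- **Direction of ratings.** A reader might also infer that ratings would fall. The app shows a numerical HRV readout as well as the trace, and irregular beats could make that readout high and look like success. The direction is unknown.
- **Feasibility in this population.** Aim 1 concerns cardiac arrest survivors in general. If some cannot use the feedback, that is a feasibility result, and excluding them in advance would hide it.
- **Unseen material.** The screening questions and the parent study's criteria are not in these documents, so a rhythm question may exist. The compliance exclusion is open-ended, and staff supervise one training session at the second video visit.

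The last item does not close the gap. The compliance exclusion works by self-selection or by what screening reveals, and someone who can follow every step has no reason to report inability. If screening does ask about rhythm, neither the criteria nor the SAP makes any use of the answer.

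**Conclusion.** The point holds in a limited form. As written, the plan admits participants without regard to rhythm or pacing, and the SAP then treats every participant's lnRMSSD slope as a measure of training. An affected slope would be misread in the proportion with a positive slope and in the three correlations with symptom change.

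The chance that this touches at least one of 10 runs from 18% to 89% over assumed rates of 2% to 20%. The conclusion rests on that assumed range and on the general physiological premise that these rhythms break or weaken the link between breathing and beat intervals.

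The harm demonstrated is confined to exploratory analyses for which the SAP claims no power. The wider inferences about task performance, Aim 1 proportions and ratings are not supported. This is a cheap improvement to the plan and no threat to the primary purpose of the pilot.

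**What to change.** 1. Add one question to the telephone and Qualtrics screens, or to the first video visit: does the participant have persistent or permanent atrial fibrillation, or a device that paces the heart all or most of the time? Record the answer, including a don't-know category.
2. Keep all participants in Aim 1 and Aim 2.
3. In the SAP's statistical approach for the Exploratory Aims, state in advance that participants answering yes are left out of the positive-slope proportion and the slope correlations, and say how don't-know answers are treated. Report the number left out, and show the all-participant result as a sensitivity analysis.

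The cost is one question and a short paragraph in the SAP. The answers rely on self-report, which may be unreliable on how often a device paces. The exploratory HRV analyses may lose one or two points. Recruitment numbers do not change, because nobody is turned away. Whether to make rhythm an exclusion is a separate design choice for the sponsor, and this point does not depend on it.

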Statistical Design and Power for Proposed Pilot Study 4:

The Care After Life-threatening Events (CALME) Study

ClinicalTrials.gov Identifier: NCT04589559

Document Date: 10/06/2020

Below we outline the statistical approach we will use to investigate the specific aims and associated hypotheses for this pilot study.

Aim 1: *To test the feasibility of a home-based heart rate variability biofeedback (HRVB) intervention in survivors of cardiac arrest (CA). Specifically, the primary purpose of this pilot study is to assess feasibility, acceptability, appropriateness, usability, and compliance for an at-home, 3-week HRVB intervention in 10 participants.*

Aim 1 will be tested by assessing the following measures:

(1) proportion of CA survivors eligible for this pilot study whom we approach and contacted who agree to participate in the trial of HRVB;

(2) proportion of participants who complete the outcome assessments at Visit 3;

(3) proportion of participants that complete a majority (≥ 8 of 15) of the at-home HRVB sessions;

(4) proportion of participants who report scores ≥ 4 for their final rating of the intervention's feasibility;

(5) proportion of participants who report scores ≥ 4 for their final rating of the intervention's acceptability;

(6) proportion of participants who report scores ≥ 4 for their final rating of the intervention's appropriateness for reducing anxiety;

and (7) proportion of participants who report total scores ≥ 68 for their final rating of the intervention's usability.

Statistical approach for Aim 1. In addition to computing the proportions listed above, we will conduct secondary analyses regarding measures 4, 5, and 6 (see above) as follows. A one-tailed t-test will be conducted comparing the mean for each scale against the comparison value of each 5-point scale's midpoint of 3.

Sample size and power estimates are based on Aim 1. Although some have used pilot studies to estimate effect sizes on primary outcomes, we agree with leaders in our field who argue that effect size estimates from small pilot studies are too imprecise to meaningfully inform effect size assumptions of power analyses for larger, later stage studies. Therefore, we do not provide power calculations for the effects of our intervention on fear-based mechanisms or behavioral outcomes. We will, however, use estimates from these studies (e.g., standard deviations, attrition rates) to help determine appropriate sample sizes for a subsequent study that is powered to detect meaningful reductions in measures of interoceptive bias.

As this is a pilot study, our sample size was guided by the need to enroll enough participants who recently survived CA to examine the feasibility of conducting a larger stage II or III randomized clinical trial of our HRVB intervention in this patient population. In particular, we will determine whether we are capable of recruiting, retaining, and assessing participants as well as implementing the desired intervention with good compliance. If the observed proportion of eligible participants who agree to participate in the trial is 40%, 50%, or 60%, and we therefore have to approach 25, 20, 17 patients, respectively, in order to enroll 10 patients in this pilot. This number is entirely feasible because the large observational trial of CA patients has enrolled 114 participants in a two-year period with eligibility criteria that largely overlap with this pilot study.

Regarding the secondary analyses for Aim 1 for feasibility, acceptability, and appropriateness, we conservatively estimate that we will have sufficient power to detect a significant difference from the three scales midpoints based on the following pilot data. In our pilot study of in-clinic heart rate variability training in patients with acute coronary syndromes, eight patients were asked to indicate to what extent they agreed with the following statement: "Based on my experience today, I believe that this procedure could be helpful for lowering feelings of anxiety." The possible responses were as follows: 1 *Strongly disagree*, 2 *Somewhat disagree*, 3 *Neither agree nor disagree*, 4 *Somewhat agree*, and 5 *Strongly agree*. We observed that a total of

Document Date: 10/06/2020

8 participants reported a mean of 4.75 ($SD = 0.46$). In a one-tailed t -test with a conservatively high comparison value of 4 (*Somewhat agree*), participants reported significantly *even more* strongly that they believed the HRVB intervention was appropriate for reducing anxiety, $t(7) = 4.58$, $p = .003$, Cohen's $d = 3.05$. This finding indicates that even just 8 participants were sufficient to detect an effect of HRVB on ratings of intervention appropriateness. This assessment is conservative given that the comparison value for the pilot data (4) was above the midpoint, whereas the comparison value for our Hypothesis 1A is the midpoint (3). The pilot data effect was detected with over 90% power, and we will require 80% power for this proposed pilot study. Therefore, we conservatively estimate that 10 participants will be sufficient to detect favorable ratings of intervention appropriateness. Similarly, we extend this rationale to the ratings of intervention feasibility and acceptability as well as usability.

Aim 2: *To assess whether cardiac-related interoceptive fear, anxiety and negative affect decrease from baseline to the 3-week visit and from baseline to the 6-week visit among CA survivors completing the HRVB intervention.*

Aim 2 will be tested by assessing the following measures:

- (1) Visit-2-to-3 change in cardiac-related interoceptive fear (measured as the within-person difference in the sum of the four cardiac-related items from the physical subscale of the Anxiety Sensitivity Index)*
- (2) Visit-2-to-3 change in trait anxiety (measured as the within-person difference in the total score of the trait version of the State-Trait Anxiety Inventory);*
- and (3) Visit-2-to-3 change in trait negative affect (measured as the within-person difference in the total score of the negative subscale of the Positive and Negative Affect Schedule).*

Statistical approach for Aim 2. We will test this aim by evaluating the change scores listed above. We hypothesize that the pattern of means will reveal a reduction in trait anxiety and negative affect. As mentioned above, this Phase-I trial is not powered to test the significance of these changes, nor is there a control comparison group to test whether the effects are caused by the HRVB intervention in this feasibility pilot study.

Exploratory Aims: *(1) To assess whether HRV increases over the course of the at-home training sessions across participants (measured as the natural log of the root mean square of the successive difference [lnRMSSD]). (2) To assess whether individual differences in the slope of change in HRV over the course of the study is positively associated with the magnitude of reduction in cardiac-related interoceptive fear, trait anxiety, or negative affect.*

Statistical approach for Exploratory Aims. (1) We will use participants' exported and deidentified HRV data to compute lnRMSSD, a standard measure of beat-to-beat HRV. For each participant, we will use a linear regression equation to find the line of best fit that represents the slope of HRV change over time for all available training sessions where time (day since baseline) is the predictor and HRV is the outcome. We will assess what proportion of participants show a positive slope (> 0). (2) We will correlate this slope with the Visit-2-to-3 change in cardiac-related interoceptive fear, the Visit-2-to-3 change in trait anxiety, and the Visit-2-to-3 change in negative affect.

Planned Interim Analyses. Given the relatively small sample size of this study ($N = 10$ participants) and the expected minimal risk of HRVB, interim analyses will not be planned. Nevertheless, if concerns arise related to adverse events, as outlined in the data safety monitoring plan, then an unblinded interim analysis may be conducted, and the trial may be stopped early.

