Distressed cardiac patients may be especially motivated to learn to influence their own heart activity in order to improve their own HRV, reduce their cardiovascular risk, and lessen their symptoms of psychological distress. Therefore, it may be wise to harness this motivation in the service of helping these patients *deliberately learn* to alter their own autonomic activity rather than simply breathing at a rate that *automatically* improves HRV without any learning process. As noted by Robert Gatchel, biofeedback “is based on the fundamental learning principle that people learn to perform a particular response when they receive feedback or information about the consequences of that response, and then make the appropriate compensatory behavior adjustments” (p. 197).[16] By providing patients with an external (e.g., visual) form of feedback about their otherwise largely

inaccessible autonomic physiology (i.e., vagus nerve activity), we will conduct a feasibility study of HRV biofeedback training with the goal of increasing HRV and reducing anxiety symptoms.

The purpose of this pilot study is to examine the feasibility of enrolling 10 participants and assessing their satisfaction with HRV biofeedback training. The data collected from participants as part of this feasibility pilot will influence the decision to submit an RO1 grant in 2021 to conduct a large-scale randomized intervention using the methods in this pilot.

2. Study Design

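### Aim 1's primary analysis is seven point proportions with no interval and no group-level criterion, on denominators of at most 10 (about 17 to 25 for uptake)

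*SAP*

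**What the plan says.** The SAP makes feasibility the primary purpose, including "compliance for an at-home, 3-week HRVB intervention in 10 participants". It states that "Aim 1 will be tested by assessing the following measures" and lists seven proportions:

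- Measure 1, uptake: "proportion of CA survivors eligible for this pilot study whom we approach and contacted who agree to participate".
- Measure 2, retention: "proportion of participants who complete the outcome assessments at Visit 3".
- Measure 3, compliance: the share completing at least 8 of 15 home sessions.
- Measures 4 to 6: the shares scoring at least 4 for feasibility, acceptability and appropriateness.
- Measure 7: the share with a usability total of at least 68.

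Under the statistical approach for Aim 1, the proportions are mentioned only in the opening clause, "In addition to computing the proportions listed above". The rest of that paragraph describes secondary one-tailed t-tests of the means of measures 4 to 6 against the scale midpoint of 3.

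The SAP's sample-size text says "we will determine whether we are capable of recruiting, retaining, and assessing participants" and refers to good compliance without defining it. It also says that estimates such as attrition rates will help to size a later study. Protocol section 1 says the pilot data "will influence the decision to submit an RO1 grant in 2021".

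**The concern.** The stated purpose is to reach a judgement on recruitment, retention, assessment and compliance, but the stated analysis stops at point estimates. Nothing in either document says how uncertain those estimates will be, or what share of participants would lead the team to conclude that the intervention or the recruitment is not workable.

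Two uses depend on these numbers: the decision to seek funding for a large randomized trial, and the attrition rate carried into that trial's sample size. With so few participants, a point estimate alone gives both uses more apparent precision than the data hold. The SAP recognises the general problem in its sample-size text, where it says that "effect size estimates from small pilot studies are too imprecise to meaningfully inform effect size assumptions of power analyses". It plans no corresponding statement of uncertainty for its own primary proportions.

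**Working it through.** **Inputs from the documents.** N = 10 (SAP, Aim 1; Protocol sections 1 and 2). Uptake scenarios of 40%, 50% and 60%, and the use of attrition rates for later sizing (SAP, sample-size text). Ratings and usability collected only at the third video visit (Protocol section 2, Measures). **Assumption:** a two-sided 95% level, because the SAP gives none. The values of x below are illustrations, not predictions.

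**1. The plan's own figure.** Number to approach = 10 / uptake, rounded up:
- 10/0.40 = 25
- 10/0.50 = 20
- 10/0.60 = 16.7, so 17

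All three match the SAP. They give the likely denominator of measure 1. They do not address the precision of any proportion.

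**2. What each stated cut-off does.**
- At least 8 of 15 sessions, a score of at least 4 and a total of at least 68 each classify one participant. None says what share of participants must qualify.
- The t-tests cover measures 4 to 6 only, are secondary, and compare a mean with 3. That is a weaker standard than the score of 4 used in the proportions. They say nothing about uptake, retention, compliance or usability.

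**3. Exact (Clopper-Pearson) 95% intervals.** Lower limit = 0.025 quantile of Beta(x, n − x + 1); upper limit = 0.975 quantile of Beta(x + 1, n − x). For x = n the upper limit is 100%.

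| Result | Estimate | Exact 95% CI |
|---|---|---|
| 7/10 | 70% | 34.8% to 93.3% |
| 8/10 | 80% | 44.4% to 97.5% |
| 9/10 | 90% | 55.5% to 99.7% |
| 10/10 | 100% | 69.2% to 100% |
| Uptake 10/25 | 40% | 21.1% to 61.3% |
| Uptake 10/20 | 50% | 27.2% to 72.8% |
| Uptake 10/17 | 59% | 32.9% to 81.6% |

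Check on 8/10: at a true rate of 44.4%, P(X ≥ 8 of 10) = 0.025, as it should be.

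**4. Dropout.** Measures 4 to 7 exist only for those who reach the third visit. With two dropouts, 6/8 (75%) has an interval of 34.9% to 96.8%.

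**5. Attrition carried forward.** For 2/10 lost, the interval is 2.5% to 55.6%. The enrolment inflation 1/(1 − attrition) is 1/0.80 = 1.25 at the estimate. At the limits it is 1/(1 − 0.025) = 1.03 and 1/(1 − 0.556) = 2.25.

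**6. How far the data can discriminate.** Binomial tails at n = 10:

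| True rate | P(X ≥ 7) | P(X ≥ 8) |
|---|---|---|
| 60% | 0.382 | 0.167 |
| 50% | 0.172 | 0.055 |
| 40% | 0.055 | 0.012 |

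**The case against.** The strongest reply is that this is a minimal-risk descriptive pilot of 10 people, and describing feasibility by proportions is legitimate. Anyone can compute a binomial interval from x and n, so omitting it hides nothing. The participant-level definitions are fixed in advance, which limits redefinition after the fact. The ratings have an inferential comparison, and the protocol says only that the data will influence the grant decision. Most of this is fair. It bears on how serious the gap is, and no larger sample is called for. It does not supply a planned statement of uncertainty for the primary outcomes, or a meaning for the promised determination.

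A reader might also infer more than the documents support:

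- **That 8/10 cannot be told apart from rates well under half.** It can: P(X ≥ 8) is 0.012 at a true 40%. The lower limit for 8/10 is only modestly under half (44.4% exact; 49.0% Wilson; 49.7% Jeffreys), and 9/10 and 10/10 exclude half. Half is in any case not a benchmark in either document.
- **That any result would be called feasible.** The SAP attaches no label to any result, so this is speculation about conduct.
- **That the SAP treats its proportions as exact.** It does not say so; it is silent on their uncertainty. Its remark on imprecision concerns effect sizes for powering later studies, so there is no contradiction.
- **That 40% uptake is the SAP's own success bar.** The word feasible there describes the number of patients to approach, supported by 114 enrolled in two years in the observational study.

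**Conclusion.** The concern holds as a gap between the stated purpose and the stated analysis. Aim 1 is described as tested and as determining capability, yet the primary analysis yields point estimates with neither an interval nor a group-level criterion. Intervals for results between 7/10 and 10/10 run from about 31 percentage points wide (10/10) to about 59 (7/10), and uptake of 10/25 has one about 40 points wide. An observed attrition of 20% is compatible with 2.5% to 55.6%, which matters for sizing the next study.

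These figures assume a 95% level, exact limits and all 10 participants in the denominator; dropout would widen them. For measure 1 the interval is approximate if patients are approached until 10 enrol: for 10/25 the upper limit would be 59.4% under that stopping rule rather than 61.3%.

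The study can run as designed. The interval is a clear and cheap improvement. The absence of a sponsor-chosen level is, on its own, missing detail rather than an error.

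**What to change.** In the SAP's statistical approach for Aim 1:

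1. Report each of the seven proportions with its numerator, its denominator and an exact (Clopper-Pearson) 95% confidence interval. Note that the interval for measure 1 is approximate if recruitment continues until 10 enrol.
2. State that feasibility, and any attrition rate carried into a later sample size, will be judged on the estimate together with its interval.
3. Replace *tested* with *estimated* for Aim 1, unless the sponsor sets a level for each measure before results are seen. If levels are set, give each one's chance of being met at a poor true rate, as in step 6 of the working.
4. Do not take 40% as the level for measure 1, since it is a recruitment scenario. Do not impose one common level on measures 2 to 7, since retention, session compliance, ratings and usability have no shared rationale for one.

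The cost is a few lines of SAP text, with no added participants, data or procedures. The downside is that reported feasibility will look less certain.
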